4.8 Intervention access

Following randomisation, both groups will be sent an email with near identical content, asking participants to either follow a web-link to read an information leaflet about SSS (control group) or follow a web-link to the StopApp (intervention group). A reminder email will be sent to all participants two weeks later. Please see procedure below for further information on when access to these materials is provided. Participants in both conditions will be told that if they wish to book an appointment at the SSS, then they are free to do so, but in taking part are under no obligation to do so. Acceptability of randomisation and the intervention will be assessed by follow-up qualitative interviews with a sub-sample of participants (see nested qualitative process evaluation below for further information on these interviews).

4.9 Procedure

The feasibility study involves two elements: A) a feasibility trial and B) a nested qualitative study. Selected participants in the feasibility trial will be invited to participate in the qualitative study at the end of baseline data collection (see below). Additionally, members of staff within recruitment settings will also be invited to participate in the qualitative study.

A – Randomised feasibility RCT

4.9.1 Procedure for participants

Please refer to Figure 1 for flow diagram illustrating participants' route through the project. Eligible smokers will be recruited from one of three settings (described above in section 4.3) and provided with a link and/or QR code to the study webpage. The study webpage is delivered via secure bespoke study management software known as 'eNgage' which is hosted on Coventry University servers (see below for information on eNgage) [https://engage.coventry.ac.uk].

Participants will be required to endorse mandatory consent statements (time/date stamped and version of participant information sheet recorded) before being able to participate. Informed consent will be obtained online in accordance with the updated General Data Protection Regulation (GDPR) guidelines.

Following consent, participants will be guided through the process of completing guestionnaires and accessing the intervention/control materials (see procedure for data management below for further detail on how this will happen). They will be asked to complete a baseline questionnaire (appendix E) which will take approximately 20 minutes to complete. They will then be randomised to either the intervention group, and then directed to the StopApp, or the control group, and then directed to the online pdf leaflet. Participants in both groups will have continued access to the content of either the intervention or the control materials (although they have been designed to be used as a one off). Two months later all participants will be asked via email to complete an online follow-up questionnaire (appendix E). Participants will also be asked if they are interested in taking part in telephone interviews to investigate the acceptability of MyWay (by endorsing a box at end of the baseline questionnaire). Consenting participants will complete one telephone interview after follow-up. Staff from recruitment settings (community and GP) will also be invited to participate in telephone interviews about their involvement in the study. See procedure for nested qualitative process evaluation below for further details (Part B; page 21).

Figure 1: Flow diagram illustrating participant's route through project.

4.9.2 Procedure for data management

Please refer to Figure 2 for a data management flow diagram. Up until the point at which all data is downloaded for analysis (see 'downloaded data' below), it will be stored online across four secure web applications as follows:

eNgage – is an online research platform owned by Coventry University (CU). It is hosted on CU's secure server and has been assessed by CU's Information Protection Unit (IPU) as meeting GDPR data protection requirements. eNgage has been developed to work seamlessly with other web applications; namely Qualtrics and Matomo (see below); these applications have been integrated using APIs (application programming interfaces) that enable data to be transferred from one application to the other. eNgage hosts details of current and previous CU research projects. These are presented as separate webpages which contain a 1) project name and summary, 2) inclusion criteria, 3) participant information details (i.e. information about the project for participants; downloadable as pdf), 4) consent statements, 5) research team names and contact details. Some consent statements are mandatory i.e. those regarding ethics issues/implications that users must indicate that they understand in order to participate. All mandatory consent statements must be endorsed by the user before a 'join project' button becomes active.

If a participant has already registered with eNgage (for participation in a previous project) then they will be asked at this point to sign-in. If they are a new user, they will be prompted to register. Registration requires users to provide their name (first name and last name) and their email address. eNgage stores for each participant that joins a project (downloadable by the lead researcher): their full name, their email address, a unique participant ID created by eNgage, the date and time at which they 'join project' (i.e. provide consent), and the version of the participant information details they consented to.

On 'joining' a project, eNgage directs participants to Qualtrics to complete baseline measures. The participant's email address is transmitted by eNgage to Qualtrics to enable auto-scheduled email invitations and reminders to be sent throughout the project at relevant time points (i.e. completion of questionnaire and access to intervention). Each participant's unique ID is also transmitted to enable all data collected within eNgage and Qualtrics to be linked (e.g. provision of consent and questionnaire responses).

The randomisation of participants to experimental conditions occurs within eNgage. After each participant has completed their baseline questionnaire within Qualtrics, eNgage will assign condition. Whilst assignment is random, the algorithm applied uses minimisation to ensure balance by factors that are likely to affect SSS access (gender, self-report socio-economic status). Data with respect to these factors is collected for each participant within the baseline questionnaire. On study set-up within eNgage, the research team specify what these factors are and their location within the baseline questionnaire (e.g. Qs1-4). eNgage retrieves this data from Qualtrics and uses it to nominate assignment. eNgage uses the participant's unique ID (sent to Qualtrics previously) to identify the individual. Each participant's response to these questions and condition assignment is additionally stored within eNgage to enable auditing of this process.

Following assignment, participants are directed to the respective intervention or control materials (both stored on the CU server). Analytics data on their use of these materials is collected by Matomo (see below). Following this, participants are directed to complete the follow-up questionnaire within Qualtrics, at 2-months after baseline.

NB. for the My Way study, there will be a number of identical eNgage project pages, one for each of the different recruitment settings. The purpose of this is to enable the unique ID created for each participant to be associated with the type of setting they were recruited from. This is necessary to assess the success of our recruitment strategy across the different settings. The URL for each page will be the only thing that is different for each project page and this will be provided accordingly for those recruited within each of the settings.

Qualtrics – is an application for creating and hosting online questionnaires. It has been assessed by CU's IPU and approval has been given for use. As specified above, Qualtrics has been integrated with eNgage to enable the collection of participant data for university research projects. All project data (baseline and followup) is held within Qualtrics until downloaded by the research team. Using the unique ID (created within eNgage and sent to Qualtrics), these two data sets can be linked together. On download, this survey data will be stored entirely separately to the eNgage data (as described above) although the unique participant ID can be used to verify that each entry (response by an individual participant to baseline and follow-up questionnaire) relates to a specific participant who provided consent. In this sense the survey data is pseudo-anonymised i.e. the eNgage data acts as a linking file which enables a data subject to be re-identified. This linking file will be retained for 6 years after the study is complete to act as a record of participant consent (see 'downloaded data' below).

Matomo – is CU hosted web analytics software that enables data on individuals' use of websites/applications to be collected (e.g. frequency and duration of visits). This will be used to collect data on each participant's use of eNgage, and either StopApp or the control website. This data is useful to identify points in the participant journey where significant drop-out occurs e.g. at the point of consent and also to examine intervention dose. This data collection will occur in the background (within eNgage and the intervention/control websites) during the project with each participant's consent. Matomo has been integrated with eNgage. Each participant's unique ID will be pushed through to this application. When analytics data is downloaded from Matomo it will be linked to the outcome data (collected via Qualtrics) for each participant using the unique ID.

PharmOutcomes/Outcomes4Health – this application is not owned by CU, not hosted on the CU server and not integrated with any of the above applications. It is owned by Pinnacle Health and commonly used for recording data by public health and primary care service providers. CU have carried out due diligence checks and confirmed that its processes are GDPR compliant. PharmOutcomes/Outcomes for Health is used by Stop Smoking Services in Warwickshire to record data on patient attendance at stop smoking appointments, guit dates and 4-week guit rates (stop smoking data). When an intervention participant using the stopapp decides that they would like to book a stop smoking service appointment and clicks on 'book now' they reach a map/service search page that asks for a postcode or town name, after the stopapp user enters the information and clicks search, the API that connects stopapp to PharmOutcomes/Outcomes4Health draws live information about which services are currently offering appointments near that location and presents the sites for the user to select from. When a site is selected, the API connecting stopapp and PharmOutcomes/Outcomes4Health pushes information from the calendar function in PharmOutcomes/Outcomes4Health about which appointments are available. The stopapp user can select a preferred time and date and an alert is sent to the relevant service provider within PharmOutcomes/Outcomes4Health about the appointment request for them to respond to. Service providers then use the PharmOutcomes or Outcomes4Health system to record all further information about the users' engagement with the service as they would for any other service client.

We will receive data for each of our participants who consented from PharmOutcomes and Outcomes4Health on whether or not they booked an appointment, whether or not they attended an appointment, whether or not they set a quit date and whether or not they achieved a 4 week quit including whether or not this was CO verified. The stop smoking service data will be sent to a secure NHS.net email address held by one member of the research team, in report format, and will include only trial participants who consented to the research team being sent information about their SSS use. This data will be recorded by hand by a researcher directly into a spreadsheet alongside each participant's unique ID generated by eNgage. Each participant's name will be used to link the data (unique ID and stop smoking data) but will not be recorded within the database. Coventry University is currently developing a data sharing agreement with Warwickshire Public Health and Pinnacle Health for this purpose. Recruitment will not begin until this (as well as all other ethics and governance approvals) is in place.

A drop-down box within the Pharmoutcomes/Outcomes4Health appointment data input form used by SSS staff, will include a compulsory prompt to staff to ask whether their client is taking part in the MyWay research project/study (with details of the trial to help recall). If the client answers yes, they will be asked if they agree (consent) to the researcher's contacting the service to collect information about their use of the service, with a 'YES/NO' drop-down box. This acts as a proof of participant consent for Pinnacle health, in order to generate a report of trial participants who provide consent only.

Downloaded data - on completion of data collection, the following will occur:

- 1) The eNgage data (to include for each participant: full name, email address, unique participant ID, the date and time consent given, the version of the participant information details they consented to, responses to optional consent questions, responses to randomisation questions and experimental condition assignment) will be retained within eNgage for six years after the end of the study to act as a record of participant consent. This data will be retained in this full form for six years after the end of the study (in case a participant wishes to make a claim against the university in which case both proof of consent plus associated data can be provided). The name and email addresses of those who provided consent (optional) to be contacted about future eNgage studies will be copied into a new datafile (marketing opt-in datafile). This data will be shared with the eNgage lead administrator who will store this on their private password protected OneDrive folder (located on CU server).
- The survey data (baseline and follow-up questionnaire responses collected in Qualtrics) will be downloaded, postcode data removed (to anonymise), and then stored on the team's shared password protected project folder (SharePoint – access rights outlined below; located on CU server)
- 3) Postcode data (taken from baseline survey) and associated unique ID to be downloaded and stored on the research lead's private password protected OneDrive folder (located on CU server). Postcode data to be converted to IMD score. IMD score to be added to downloaded baseline survey data (linked to participant ID). Postcode data will be retained until the end of data processing (data analysed and findings reported) and then deleted.
- 4) The analytics data (from Matomo) will be downloaded and stored on the team's shared password protected project folder (SharePoint – access rights outlined below; located on CU server); NB this data is anonymised IP address masked by default.
- The project stop smoking data will be stored on the team's shared password protected project folder (SharePoint – access rights outlined below; located on CU server)
- 6) In preparation for analysis, data from 2, 3, 4 and 5 will be linked using each participant's unique ID to create the complete datafile in preparation for analysis; initially this will be within Excel format but will likely also be exported

to SPSS (all data will however remain within the shared password protected project folder)

- Research team to agree that all required data (in required format) present/complete and then all research data will be permanently deleted from Qualtrics and Matomo
- 8) The complete datafile (anonymised data created in step 6 above) will be retained for six years after the study has ended (the source files 2, 3, 4 and5) will be deleted

Data access rights:

Sharepoint project folder – accessible to the research team (CU: [name], [name], [name], [name], [name], [name], [name]; external: [name], [name], [name])

eNgage – accessible only to CU members of research team with eNgage administrative rights ([name], [name], [name], [name], [name], [name]); permissions (editing rights) vary however.

Matomo – accessible only to CU members of research team ([name], [name], [name], [name], [name], [name])

Qualtrics – accessible only to CU members of research team ([name], [name], [name], [name], [name], [name])

Figure 2: Flow diagram of data management (* web analytics data collected by Matomo)

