3.2 Primary Objective

To conduct a feasibility trial of StopApp to estimate recruitment and attrition rates of participants across three settings: GP surgeries, community settings and on-line; at baseline, intervention access, and two-month follow-up.

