4.2 Setting and Participants

Smokers who are aged 16 years and over will be recruited from 3 settings across Warwickshire including 4 GP surgeries, a range of community settings (e.g. pharmacies, children's centres, libraries) and online. All current smokers aged over 16 years registered with participating GP practices in Warwickshire, or accessing participating community services or viewing advertising for the study online, will be invited to take part in the feasibility trial.

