4.3.1 GP surgery recruitment

The study is eligible for adoption to the NIHR portfolio and the process of application has begun. We will apply for joint primary care and public health portfolio status. The Clinical Research Network (CRN) are supporting recruitment via GP surgeries. GP practices in Warwickshire have been invited to participate and of those who are interested, we will select four for the feasibility trial (stratified by indices of Deprivation, to ensure we are reaching diverse groups). Patients listed as smokers on the practice records will be checked by practice staff to ensure they meet the inclusion criteria (see 4.4 below) of being aged 16 years or older and a smoker. To remove the chances of contamination, we will contact one smoker per household only. Where two or more smokers cohabit, the resident whose first name is alphabetically first will be selected for invitation to the study and the other resident(s) will receive the control intervention (a web-based pdf with stop smoking service information) after the study has ended. Note: the reason for non-selection will not be provided to the co-habiting smoker to avoid disclosing that the selected resident is a smoker or participating in the study.

Smokers (one smoker per household) will be sent an email and/or text or letter (dependent on GP and patient communications set up) from their GP inviting them to take part in the 'MyWay' study. This will inform them that the study will investigate the best ways of using the internet to help people to stop smoking. Where a GP practice's preferred method of contact with patients is via postal letter, Docmail services will be used to distribute letters as recommended by the CRN. For ethical reasons we will not attempt to recruit people aged less than 16 years as they would typically require parental consent to participate in research and parents may not be aware of their child's smoking status. The email/text/letter (see appendix M & N) will include brief information and a web link/QR code to the study website where further

information and the secure electronic consent process can be accessed (see section 4.9 Procedure below for further information).

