4.3.2 Recruitment from other community settings

Contact has been made with the county council leads for libraries, wellbeing hubs, all pharmacies and all children's centres in Warwickshire, and with the family information service and the registrar's office in order to provide information about the proposed study and gain in principle agreement to support recruitment. We have so far gained in principle support from four pharmacies, over 30 children's centres, all seven wellbeing hubs, the family information service and the registrar's office and will be acting on further suggestions from our PPI group for community recruitment locations (e.g. dentists). Following suggestions from our PPI group, we will also be including bus stop and bus based advertising to aid recruitment.

We will supply each participating community setting with posters to display in prominent locations advertising the 'MyWay' study with contact details of the research team and a community-setting specific QR code to gain immediate access to the study website for participants. We will train all staff in participating locations about the study to enable them to answer any basic queries and to promote it confidently. We will also combine staff promotion of the study via leaflets and a very brief verbal introduction with ad hoc research assistant presence for active promotion and recruitment on site. Where staff provide a leaflet, access to the study will be either through QR code/web link to project website or via contact with the research team. Where a research assistant recruits on site, physical copies of the participant information sheet will be available and immediate access provided to the study via tablet computers. People will have the option to gain access to the study but consider participation and return later to the website to provide informed consent.

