4.3.3 Online recruitment

The marketing and communications team at Warwickshire County Council (WCC) will be supporting all online recruitment activities. Specifically, they will provide support for online promotion of the study via social media, targeted email marketing, Google advertising and all WCC internal and external channels such as press releases and electronic newsletters. Social media will include Facebook ads as well as via their standard social media channels including twitter feed, Facebook pages and web pages. These ads will appear to anyone in the Warwickshire area searching for health-related products or services. We will run a three-month long campaign to advertise the study. In addition, participating community settings including children's centres, pharmacies and wellbeing hubs will also promote the study online via their communication channels including social media such as Facebook and twitter. Anyone hearing about the study via this method will be able to link directly to the study website.

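### Setting is recorded only by the web address used, so with overlapping channels the per-setting rates measure route of entry and may not show which setting prompted it

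*Protocol*

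**What the plan says.** The primary objective (Protocol 3.2) is to "estimate recruitment and attrition rates of participants across three settings: GP surgeries, community settings and on-line". Section 4.9.2 describes how setting is captured: "there will be a number of identical eNgage project pages, one for each of the different recruitment settings", so that each participant's ID carries a setting. It adds that "The URL for each page will be the only thing that is different for each project page" and, of this arrangement, that "This is necessary to assess the success of our recruitment strategy across the different settings".

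The settings share one area. Under 4.2, smokers "will be recruited from 3 settings across Warwickshire including 4 GP surgeries, a range of community settings" and online. Their channels also overlap:

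- Section 4.3.3 describes social media and search advertising aimed across the county, and says that "participating community settings including children's centres, pharmacies and wellbeing hubs will also promote the study online via their communication channels". It does not say which page address those posts carry.
- Section 4.3.2 places public transport advertising under community recruitment: "we will also be including bus stop and bus based advertising to aid recruitment".
- Section 4.3.1 has the four practices invite their listed smokers directly. It states: "To remove the chances of contamination, we will contact one smoker per household only".

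Section 4.12 defines the GP rate as recruits over the smokers found on the practices' lists. The community and online results are the time and spend needed to reach 54, or the number and spend over three months. Section 6 rests the decision largely on whether at least one setting could supply the main trial, with an average of 1.8 participants per day as its only number.

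**The concern.** A page address shows how someone arrived. It shows what brought them only if each person meets one channel. Here a smoker on a practice list can receive the GP invitation and also see an online advert or a bus poster, and no rule is given for a person reached twice.

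The GP rate is the most exposed because its denominator is fixed by the lists. The per-setting figures are what a funder would use to choose routes for the definitive trial, and the source of awareness cannot be recovered reliably if it is not asked at entry.

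Two related gaps follow from the parallel pages and open routes. First, no check is described for the same person joining on two pages before randomisation. Section 4.9.2 links stop smoking service records to the study ID by name, so one service record could match two IDs, possibly in different arms. Second, the household rule governs GP invitations only. Under 4.4 a cohabitant may self-identify through a community or online route, and nothing in 4.5 excludes them.

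**Working it through.** **Inputs.** Protocol 4.11: 980 participants for a definitive trial, 18 months, 1.8 per day, three months of feasibility recruitment, 162 in total, 54 per setting. Protocol 4.12: definitions of the rates.

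**The plan's own figures.** 980 / 540 days = 1.81 and 980 / 547.5 days = 1.79, so 1.8 per day reproduces. 1.8 × 90 = 162, 162 / 3 = 54, and 54 / 90 = 0.6 per day per setting. Reaching 54 in each setting within one three-month period implies that the settings run together.

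**GP rate.** Let N be the number of smokers on the lists and m the share of GP-prompted recruits who enter by another page. The recorded rate is 54(1 − m)/N against 54/N, a ratio of 1 − m whatever N is. That path lowers the GP rate by the fraction m. Someone prompted by an advert who then uses the GP link raises it. The documents give neither flow, so the net direction is unknown.

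**Crossover between two settings.** The documents give no crossover share, so m is an assumption shown as a range. Suppose each of two settings truly prompts 54 recruits and a share m of one enters by the other's page. Recorded counts are 54(1 − m) and 54(1 + m), each divided by 90 for the daily rate. With spend held fixed, cost per recruit is multiplied by 1/(1 − m) in the setting that loses recruits and by 1/(1 + m) in the one that gains them.

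| Assumed m | Recorded counts | Per day | Cost per recruit, losing | Cost per recruit, gaining |
|---|---|---|---|---|
| 5% | 51.3 v 56.7 | 0.57 v 0.63 | +5% | −5% |
| 10% | 48.6 v 59.4 | 0.54 v 0.66 | +11% | −9% |
| 20% | 43.2 v 64.8 | 0.48 v 0.72 | +25% | −17% |
| 30% | 37.8 v 70.2 | 0.42 v 0.78 | +43% | −23% |

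In every row the two counts add to 108. With the third setting's 54 the total stays at 162, or 1.8 per day.

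**Duplicates.** If a share d of 162 records are second entries by the same person, the number of people is 162(1 − d) and the true rate is that number over 90. The share is again assumed:

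- d = 1%: 160.4 people, 1.78 per day.
- d = 5%: 153.9 people, 1.71 per day.
- d = 10%: 145.8 people, 1.62 per day.

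**The case against.** The strongest reply is that route of entry is a legitimate definition of setting and that the plan takes steps to make it work. Each setting's address is given to the people recruited there, community posters carry their own QR code, and GP invitees receive a link with the invitation. The study means to test channels in realistic use, so some overlap is intended. This stands as far as it goes. What is missing is a statement that setting means route of entry, and a way to see how far it departs from source.

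A reader might infer several stronger things that the documents do not support:

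- **That the rates are misattributed, with GP biased down and online up.** Only a risk is shown, and crossing can go either way.
- **That posts by community sites are counted as online.** Section 4.3.3 files them under online recruitment but does not say which address they carry.
- **That spend is credited by web address.** Section 4.9.2 ties only the participant to a setting; cost data are gathered separately under 4.10.3. Cost per recruit is affected only through the recruit count.
- **That one person can join twice.** This is not ruled out, but it is not stated. Accounts use name and email with sign-in, so duplicates could be detected. Whether eNgage already blocks a second join is unspecified.
- **That the 1.8 per day criterion fails.** Crossover does not move it, and section 6 sets no threshold per setting.

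The questionnaire in Appendix E is not shown and may already ask how people heard of the study; the baseline items listed in 4.10.1 do not include such a question. The household point is separate: it bears on the comparison between arms, not on recruitment rates.

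**Conclusion.** The point holds as a limitation of measurement that touches the primary objective. The per-setting recruitment and attrition figures describe the page used. Given shared territory and overlapping channels, they may not describe the setting that prompted entry. The clearest case is a GP-listed smoker who enters elsewhere and is lost from the GP numerator only.

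The size cannot be derived from the protocol. Under an assumed crossover of 5% to 30% of 54, two settings with equal true rates of 0.6 per day would appear as 0.57 v 0.63 up to 0.42 v 0.78. That could change which route looks best for a definitive trial, while the overall 1.8 per day stays put. Only duplicates move the overall figure: an assumed 1% to 10% among 162 records means a true 1.78 to 1.62. The statement in 4.3.1 that contamination is removed is too strong, because the rule does not reach the other two routes.

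**What to change.** 1. In 4.9.2 and 4.12, define setting as route of entry, and state which page address the community sites' online posts carry.
2. Add one tick-all baseline item on where the participant heard about MyWay, unless Appendix E already has one. Options: GP invitation, community site or its staff, bus advertising, a community site's social media, other online.
3. Report recruitment and cost per recruit by page address and by reported source, with the overlap. Include the number who report a GP invitation but entered by another page.
4. Before randomisation, check email across all MyWay pages. Flag name matches for review and do not refuse them automatically, since two people can share a name. Matching surnames to postcodes is not needed and would cut across the plan's separate storage of the two.
5. Reword 4.3.1 to say that contamination is reduced among GP invitees only.

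The cost is one question, one check in the software, one extra table and some wording, all to be in place before recruitment opens. The downside is that recall of source is imperfect, so the item supplements the page address and does not replace it.
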